1.4. Superior Hypogastric Nerve Block

Because of the difficulties dealing with pain post UAE, recently a group in Ottawa has applied a technique used previously to treat chronic pelvic pain from pelvic tumors to control the acute pelvic pain associated with UAE[6]. This consists in doing a nerve

block at the superior hypogastric nerve plexus using a long acting anesthetic agent called bupivacaine. The medication has a duration of action of 4-8 hours which can cover the first high pain plateau until the lower pain plateau is reached. Using the hypogastric nerve block and an aggressive PO analgesia protocol, they have been able to obtain a 100% discharge from the hospital with patients feeling only mild or no pain at time of discharge. There was a 5% readmission rate due to pain. Their results suggest a significant improvement in pain control compared to same-day discharge protocols without a superior hypogastric nerve block.

The hypogastric nerve block consists of advancing a tiny 21 or 22-gauge needle through the abdomen up to the anterior surface of the vertebral body located below the aortic bifurcation. This is the location of the superior hypogastric nerve plexus. Once there, the anesthetic agent is administered. The potential most serious risks of the procedure would include transgression of bowel loops, leading to theoretical transport of bacteria out of the bowel into the abdomen and associated infection, and intravascular injection of the anesthetic agent, which can lead to cardiac arrhythmias and seizures. In order to limit complications from intravascular injection of contrast, we have opted to use ropivacaine as the anesthetic agent, an agent with better safety profile if intravascular injection occurs and similar duration of action[7]. As well, the use of epinephrine in the anesthetic agent can help identify an intravascular injection by monitoring for an increase in heart rate. Finally, prior to injecting the anesthetic agent, we inject a contrast agent that allows us to identify an intravascular injection under fluoroscopy (which is used for the UAE procedure). The group from Ottawa has had no complications, beyond those that can be explained by the UAE procedure itself, in their published series of 139 patients[6] as well as in the more than 400 patients they have treated so far (personal communication). We have also performed approximately 30 of these procedures, without complications.

Because of the success of the group in Ottawa in performing the SHGNB, we have just recently started to offer this procedure as well. Initial results are also very encouraging with recovery nurses informing us that in general the patients seem to be doing much better with the nerve block in place. However the data remains anecdotal. There have been no studies to date comparing simple oral/IV sedation to SHGNB + oral/IV sedation. For this reason, probably, the procedure has been very slow to be adopted by people who perform UAEs. We believe that, to put this issue to rest, there is a necessity for such a comparative trial and, especially important in the context of a subjective outcome such as pain, it is our belief that a randomized double-blinded control trial is needed to obtain conclusive data. This was the reason this study was put together.

2. Research Question:

Is there a difference in subjective pain score patients experience and in the need for analgesics post uterine artery embolization for fibroids if the patients undergo a superior hypogastric nerve block during the embolization procedure.

3. Objectives:

The primary objective is to assess:

- Reduction in subjective pain as measured by patient self administration of visual analogue scale and reduction in use of oral analgesics at home and IV/oral analgesics while in hospital

The secondary objectives are:

- Differences in adverse events between groups with and without SHGNB
- Differences in pain/complication related admissions between groups with and without SHGNB
- Differences in pain in relation to total volume of fibroids between groups with and without SHGNB
- Differences in pain in relation to fibroids vs. adenomyosis between groups with and without SHGNB
- Differences in successful outcome of the embolization both by imaging and clinically between groups with and without SHGNB
- Differences in admission rates
- Differences in rates of return visits to ER for pain issues
- Patient use and appreciation of the online pain survey

4. Implications:

This comparison trial will provide important new information regarding the role SHGNB could play in pain control in women post UAE. The expected benefits would include increasing the availability of UAE in centers with the radiology resources to offer the procedure but without the ability to admit patients overnight and to some patients for whom pain has been a strong deterrent to proceed with UAE and who want to avoid hysterectomy. In addition, another benefit, if proven to allow increased same day discharge, would be to decrease the admission rate post UAE which could have benefits both for the patient as well as for the hospital, in terms of admission bed management, nursing time and medication usage, and at a financial level.

If the procedure is found not to have benefit, this study will give basis to avoid placing patients at risks of complications from an unnecessary added procedure.

5. Data analysis and sample size Calculation

▪ Data gathering and analysis

Nurses in the recovery room will be provided a specific medication escalation regimen to follow based on a patient-centered pain requirement protocol. At the time of discharge, the patient will be seen by the IRMD who will gather the data regarding the dose and frequency of use of analgesia while in the recovery room. He will review the visual analogue pain scale chart with the patient and get her to rank the pain between a scale of 0 to 10 for the pain felt immediately after the procedure, 2 hours after the procedure has ended, and immediately prior to discharge. The recovery nurses will also have a routine pain scale evaluation prior to giving medication and these will be reviewed. The patient will also be given a folder with a series of sheets of visual pain scales to fill out 3 times a day, at specific times while at home, for up to 10 days. They will be provided with a stamped envelope to return to us once they are all filled out. Alternatively, the patient will be offered an anonymous login ID that will allow them to fill out the forms by internet (using a Canadian based survey web site).

The data will be gathered. Confirmation of the data distribution will be done. A normal distribution is expected, but statistical analyses will be modified

accordingly. We expect that the data analysis will consist of regression analysis of the temporal pain level distribution between the group with and without the SHGNB. Continuous variable data, with normal distributions, subgroup analysis of the secondary objectives will be compared using a Student's t- test.

▪ **Sample size calculation**

Sample size calculations are based on published data showing the average pain felt by ladies post uterine artery embolization being of 7/10 with a standard deviation of approximately 2.5. The published study of SHGNB for UAE demonstrated a decrease in pain from 7 to 5-2 depending on the analgesics regimen used [6]. We opted for the conservative drop in pain scale from 7 to 5 with a standard deviation of 2.5. This gives an effect size of 0.8. With type I error (alpha) set at 0.05 and type II error (beta) set at 0.2 (power of 80%), the sample size calculations yields a needed sample size of 42. We expect up to a 20% drop out rate due to loss to follow-up, giving a total sample size needed of 50, leaving 25 patients per group. [8]

If the analysis of the data after recruiting 50 patients is highly suggestive of an effect but without statistical significance, and if the calculations suggest we could get statistical significance by doubling the number of participants, and there have been no significant adverse events from the nerve block, we would increase the number of patients to 100. If adverse events have occurred, the number would not be increased unless approval by the ethics committee.

▪ **Interim analysis**

The previous sample size has been calculated with a conservative number, but the decrease in pain can be as large as from 7 down to 2 based on previous studies. Therefore the above estimation may necessitate more patients than are needed to prove clinical worthiness of the procedure. Clinically, our group feels that we would proceed with the block if we could get at least a 50% decrease in pain from 7 down to 3.5 (a scale of 4 being the common number used for discharge of patients from the recovery room). If a similar sample size calculations is performed for such a drop, a total sample size of 16 would be needed. With a similar drop out rate it is our feeling that an interim analysis should be performed at a patient study completion number of 20, so as to avoid recruiting an excessive number of patients to prove the value of the procedure. Therefore we would perform an interim analysis at 20 patients having completed the study. If the data is statistically significant the study would be terminated early.

6. Study Population

The target population who will be included to participate in this study is all women referred to us for a UAE procedure.

6.1. Inclusion criteria:

1. Women with symptomatic fibroids or adenomyosis that have requested and been approved for uterine artery embolization
2. Women age 35-60 y.o.
3. Ability to comply with the requirements of the study procedures

6.2. Exclusion criteria:

1. Patients in whom the vascular anatomy prevents access to the superior hypogastric nerve plexus safely
2. Patients who have known allergy to the anesthetic agent
3. Patients with signs of skin infection at the entry site of the needle used to place the nerve block
4. Patients with signs of infection such as fever
5. Patients with history of inflammatory bowel disease or with signs of colitis
6. Patients with uncorrectable abnormal coagulation status (INR >1.5 and plt < 50000 without use of anticoagulation agents)
7. Patients with preexisting conditions, which, in the opinion of the investigator, interfere with the conduct of the study.
8. Patients who are uncooperative, cannot follow instructions, or who are unlikely to comply with follow-up appointments or fill-out the post-procedural pain questionnaires.
9. Patients with a mental state that may preclude completion of the study procedure or is unable to provide informed consent

6.3. Randomization:

A block randomization will be used to assign patients to either the SHGNB or to the sham procedure group. Randomization will be performed using a randomization program and the results placed in independent envelopes. These envelopes will be opened based on order of inclusion into the study and will determine the group in which patients will be placed.

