
Planned Sample Size
	
Based on published data, the average pain felt by ladies post uterine artery embolization is 7/10 with a standard deviation of approximately 2.5. The published study of SHGNB for UAE demonstrated a decrease in pain from 7 to 2-5 depending on the analgesics regimen used. We

	
opted for the conservative drop in pain scale from 7 to 5 with a standard deviation of 2.5. This gives an effect size of 0.8. With type I error (alpha) set at 0.05 and type II error (beta) set at 0.2 (power of 80%), the sample size calculations yields a needed sample size of 42. We expect up to a 20% drop out rate due to loss to follow-up, giving a total sample size needed of 50, leaving 25 patients per group.
 
Since the pain drop can be more significant than the conservative value we have opted to use, we suggest an interim analysis that would be expected to give us statistical significance if the pain scale was improved by 50% from 7-3.5 (4 being the number usually used by the recovery room to decide to release patients). Based on similar calculations, to show this level of improvement (taking in account a similar drop out rate), one would need a total of 20 patients and therefore we plan on doing an interim analysis at 20 patients having completed the study to see if there is any need to continue the study or not.

Inclusion Criteria	
 1. Women with symptomatic fibroids or adenomyosis that have requested and been approved for uterine artery embolization 2. Age of patients ranging between 35 and 60 years old 3. Ability to comply with the requirements of the study procedures

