Exclusion Criteria	
 1. Patients in whom the vascular anatomy prevents access to the superior hypogastric nerve plexus safely 2. Patients who have known allergy to the anesthetic agent 3. Patients with signs of skin infection at the entry site of the needle used to place the nerve block 4. Patients with signs of infection such as fever 5. Patients with history of inflammatory bowel disease or with signs of colitis 6. Patients with uncorrectable abnormal coagulation status (INR >1.5 and plt < 50000 without use of anticoagulation agents) 7. Patients with preexisting conditions, which, in the opinion of the investigator, interfere with the conduct of the study. 8. Patients who are uncooperative, cannot follow instructions, or who is unlikely to comply with follow-up appointments or fill-out the post-procedural pain questionnaires. 9. Patients with mental state that may preclude completion of the study procedure or be unable to provide informed consent
Schedule of Study Visits	
No change from routine schedule presently used:
 
 1) MRI pre-UAE 2) Consultation pre-UAE (consent will be obtained at this time) 3) UAE procedure (not usually the same day as the consultation) 4) MRI 4-6 months post-UAE 5) Consultation post-UAE after post-UAE MRI completed
Efficacy Outcome	
 ▪ Primary: 
 ○ Reduction in pain as measured by patient self administration of visual analogue scale

	
 ○ Reduction in use of oral analgesics at home and IV/oral analgesics while in hospital ▪ Secondary: Comparison of sham versus SHGNB group to look for 
 ○ Differences in adverse events ○ Differences in pain/complication related admissions ○ Differences in pain in relation to total volume of fibroids ○ Differences in pain in relation to fibroids versus adenomyosis ○ Differences in successful outcome of the embolization both by imaging and clinically ○ Use of the online questionnaire vs the paper questionnaire

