Data integrity will be maintained throughout the study. Logic rules within the database will be used to maximize integrity, and random data validation checks will be performed routinely. The research investigator will review studies and patients' data on a monthly basis to ensure that patient follow-up is proceeding as expected. All cases where the research investigator finds a discrepancy in imaging interpretation or outcome assessment will be reviewed by the Adjudication Committee, consisting of the principal investigators. An independent radiologist from the MUHC will be asked to determine the outcome of a dispute amongst the Adjudication Committee.

8. Data Analysis:

Data will be collected and tabulated using the commercially available JMP10/SAS statistical analysis software (SAS Institute Inc., Cary, NC, USA). Descriptive statistics will be provided for the efficacy outcome results and will be presented in terms of percentage, frequency, means and 95% confidence interval of the means. Differences between both groups will be compared using the Chi-square test for categorical variables and Student's t- test for the continuous variables. ANOVA test and multivariate logistic-regression analysis will be used to compare interplay of more than two variables. Two-tailed p-values of less than 0.05 will be set for statistical significance.

9. Ethical considerations:

Research Ethics approval from the MUHC Research Ethics Board office will be obtained prior to the commencement of the study or related research procedures. All patients will be informed about the data that will be gathered for the study. All patients will have the ability to refuse participating in the study as soon as they are able to evaluate it and give their approval or not. Patients will always be given options to ask questions at any time and questions will be answered in a non-intimidating way so as to try to avoid influencing the patient's decision. At any time, the patient can decide to remove himself from the study. If this is the case, he will receive the standard of care.

No unique patient identifying data will appear on the sheets that will be coded only by study identification number. A key linking the patient name and study identification number will be maintained in a separate database. All datasheets will be kept in a locked, dedicated research office. All computer records will be maintained in a

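### Repeated testing at an unadjusted 0.05 (20, 50 and possibly 100 patients) takes the error for pain alone to about 8–10%, and two primary outcomes have no rule linking them

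*Combined protocol and SAP*

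**What the plan says.** **Outcomes.** Section 3 joins pain and analgesic use in one primary objective: "Reduction in subjective pain as measured by patient self administration of visual analogue scale and reduction in use of oral analgesics at home", followed by in-hospital drugs. The synopsis (Efficacy Outcome) lists analgesic use as a separate primary bullet: "Reduction in use of oral analgesics at home and IV/oral analgesics while in hospital". Section 5 collects three in-hospital pain scores (just after the procedure, at 2 hours, before discharge) and a home diary. None of these, and no summary of them, is named primary. Appendix III records analgesics drug by drug, with no common unit.

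**Analysis.** Section 5 expects "regression analysis of the temporal pain level distribution between the group with and without the SHGNB". Section 8 lists general tests and one level: "Two-tailed p-values of less than 0.05 will be set for statistical significance". The sample size in Section 5 rests on a single pain comparison, 7 versus 5 with SD 2.5.

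**Looks at the data.** The synopsis sizes the interim at 20 patients to reach "statistical significance if the pain scale was improved by 50% from 7-3.5". Section 5 gives the stopping rule: "If the data is statistically significant the study would be terminated early". At 50 patients, Section 5 allows an increase to 100 if the result is "highly suggestive of an effect but without statistical significance", if calculations point to significance with twice the patients, and if the block has caused no significant adverse events.

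**The concern.** A trial that tests at 20, again at 50 and perhaps at 100, each time at 0.05, has two or three chances of a false positive. The error is then above 5% even if pain is the only outcome that counts.

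The two primary outcomes add a second gap. Nothing says whether success needs pain, drug use, either or both, or which pain score or summary is tested. These choices could be made after the data are seen. An either rule raises error; a both rule lowers power. The protocol wants this trial to settle the question, so a positive result should not be open to challenge on these grounds.

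**Working it through.** **1. The plan's own figures.** d = 2/2.5 = 0.8. A t-test with 80% power needs 21 per arm (42 in total) one-sided, which matches the plan, and 26 per arm (52) two-sided. The interim, d = 3.5/2.5 = 1.4, gives 8 per arm (16) one-sided, also a match. The one-sided sizing against a two-tailed analysis is a separate inconsistency. It matters here only because two-sided power for one outcome is 69.3% at 20 per arm and 79.1% at 25 per arm.

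**2. Numbers per arm.** The interim has 20 completers, 10 per arm. The main analysis has 25 per arm without loss (suits scores taken before discharge), or 50 × 0.8 = 40, so 20 per arm. The extension doubles these to 50 or 40 per arm.

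**3. Extension trigger.** If the observed effect persists, doubling the sample multiplies z by √2. Significance at 0.05 then needs z ≥ 1.96/√2 = 1.386, or p ≤ 0.166 (0.167 with t). The undefined *highly suggestive* condition can only narrow this, so a range of p < 0.10 to p < 0.17 is assumed.

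**4. Error for one pain outcome.** Error = P(p₁ < 0.05, or p₂ < 0.05, or [p₂ < trigger and p₃ < 0.05]) under no effect, with two-sided t-tests on accumulating normal data (2,000,000 simulated trials).

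| Per arm | Interim + 50 | + extension, p < 0.10 | + extension, p < 0.17 |
|---|---|---|---|
| 10/20/40 | 8.4% | 9.1% | 9.7–9.8% |
| 10/25/50 | 8.7% | 9.4% | 10.1% |

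**5. Two outcomes** (correlation 0 to 0.7 assumed; 200,000 simulated trials).
- Either may win, 20 per arm, one analysis: about 1 − 0.95² = 9.75% if independent, 8.4% at correlation 0.7. With the interim: 16% falling to 14%.
- Both must win, d = 0.8 for each: 0.693² = 48% (20 per arm) and 0.791² = 63% (25 per arm) if independent, rising to 58% and 70% at correlation 0.7.

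**6. Levels that hold 5%.** With a final level of 0.02, Section 5's doubling condition becomes z ≥ 2.326/√2 = 1.645, or p ≤ 0.10. Testing at 0.003, then 0.04, extending for p from 0.04 to 0.10 and then testing at 0.02 gives a total error of 4.6% for both sets of sizes. The chance of extending under no effect is 5.9%. Without an extension, 0.003 then 0.0487 gives 5.0%.

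**7. Power cost.** One score, d = 0.8, tested at 0.04: 66% (20 per arm) or 76% (25 per arm), against 69% or 79% at 0.05. Interim at 10 per arm, d = 1.4: 84% at 0.05, 42% at 0.003.

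**8. Mean of the three in-hospital scores** (one candidate measure). Its SD is 2.5 × √((1 + 2ρ)/3), with within-patient correlation ρ = 0.3–0.7 assumed. Power at 0.05, over 20 to 25 per arm:
- 2-point difference at all three times: 79–97%.
- None at discharge (mean difference 4/3 = 1.33): 45–72%.
- Only at 2 hours (mean difference 2/3 = 0.67): 15–24%.

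**9. Forms.** Home diary: Section 5 gives up to 3 × 10 = 30 readings; Section 7.5 gives 3 × 3 + 7 = 16. Appendix III has timed arrival and departure scores and a score at each dose, but no 2-hour field.

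**The case against.** Much of the plan can be read more kindly.

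- **Pain is the implied lead.** Both the main sample size and the interim are sized on pain. A reader might infer that the interim has no outcome at all; the sizing does not support that. But pain alone still gives 8.4–8.7%, because the level is not adjusted.
- **The *and* in Section 3 leans towards requiring both outcomes.** A reader might infer that the trial's error is 14–16%. The documents do not support that as a finding: it holds only under an either rule, which they never state. The power loss under a both rule then applies instead.
- **Regression leads for pain.** A reader might see a direct conflict between Section 5 and the "t- test for the continuous variables" in Section 8. That overstates it: Section 8 is generic, and Section 5 ties the t-test to subgroup analysis of the secondary objectives. What remains is that the regression has no stated window or tested term.
- **The extension is not open-ended.** It has a doubling condition and an adverse-event condition. That is why the range above stops at p < 0.17, but its main efficacy condition still has no number.
- **Scores are collected.** A reader might infer that the 2-hour score is never recorded, or that all early scores rest on recall. Section 5 has a pain chart and nurse scores reviewed at discharge, and Appendix III times the arrival score. The missing 2-hour field is a gap in the form only.

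**Conclusion.** The point stands. With pain as the sole outcome, the planned looks give a type I error of 8.4–8.7%, and 9.1–10.1% with the extension, instead of 5%. The first range needs no assumption about analgesic use; the second depends on the assumed trigger. The missing rule for two primaries is a real gap under either reading, but its size depends on the rule chosen, the assumed correlation and, for power, d = 0.8 for drug use, for which the plan gives no effect size. The diary counts and the 2-hour field are minor consistency points. This should be changed before any outcome data are examined.

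**What to change.** 1. **Set levels for pain at each look.** For example, two-sided p < 0.003 at 20 and p < 0.04 at 50; extend only if p at 50 lies between 0.04 and 0.10 and the existing adverse-event condition holds; then p < 0.02 at 100. If the extension is dropped, use 0.003 then about 0.0487.
2. **Name one primary pain measure and its test** before any data are seen. The choice is the sponsor's; the three-score in-hospital mean is one example. If regression is kept, state the window and the term tested. Test analgesic use, in a stated common unit, next in fixed order.
3. **Reconcile the diary schedules** in Sections 5 and 7.5, and add a timed 2-hour pain field to Appendix III.

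The cost is protocol wording, one form field, and no patients beyond the 50 or 100 already planned. The downsides are these:
- If pain truly falls from 7 to 3.5, the chance of stopping at 20 on one score is halved.
- Testing at 0.04 costs about 3 points of power at 50 patients.
- Analgesic use cannot succeed alone.
- If an in-hospital measure is chosen, both home pain and home analgesic use become secondary.
- A three-score mean pays off only if the benefit spans all three times. It does badly if the block acts only around 2 hours, so the sponsor should weigh that before choosing it.

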1.3. Pain from Uterine artery embolization

When UAE was first started, the need for pain control was evident. Although it was initially done with general anesthesia in the USA, it was quickly found that this was not necessary. However almost everyone admitted the patient overnight with morphine based patient controlled analgesia (PCA). The use of PCA pumps allowed careful assessment of the pain course after UAE. The information gathered shows a maximal pain threshold reached at approximately 2 hours post-procedure, which lasts 3-4 hours and then a gradual decrease to a lower plateau over another 4-6 hours. This period of decrease to a lower pain plateau is the time during which attempts at discharging the patients from the hospital with oral pain medication is attempted [5]. Most women declare no longer having embolization related pain after 7-10 days.

Because of limited availability to hospital admission after radiological procedures at the MUHC, and the need to offer this less invasive treatment of uterine fibroids to women, the interventional radiologists at the MUHC have offered the procedure with an aggressive IV/Oral sedation protocol while in recovery and discharge orders 4-5 hours after the end of the procedure. The patients are sent home with oral pain medication. However despite this aggressive protocol, approximately 5-10% of patients need admission, not without difficulties at times due to the chronic shortage of beds. This is primarily because this time point of attempted home discharge from the recovery room is still in the phase where the lower more tolerable pain plateau, usually reached only approximately 8 hours after the procedure, has not been reached yet. Even in those that are successfully sent home, they report significant discomfort upon discharge from the hospital and there are some that return to the emergency department for pain management.

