Appendix III - At discharge from recovery room

Identification code: _____

Date of UAE: _____ (YY/ MM / DD)

RVH/MGH # _____ Age: _____

Pain scale at time of arrival to recovery (0-10): _____ (time: __:__)

IV Medications used during recovery (Dose/ time/pain scale at time of giving it):

Fentanyl (Dose/Time): _____ ug _____:_____ /10
 _____ ug _____:_____ /10
 _____ ug _____:_____ /10
 _____ ug _____:_____ /10
 _____ ug _____:_____ /10

Midazolam (Dose/Time): _____ mg _____:_____ /10
 _____ mg _____:_____ /10
 _____ mg _____:_____ /10
 _____ mg _____:_____ /10
 _____ mg _____:_____ /10

Other (Name/Dose/Time): _____ :_____ /10
 _____ :_____ /10
 _____ :_____ /10

Oral Medications used during recovery (Dose/time/pain scale at time of giving it):

Empracet: _____ / _____ : _____ / _____ /10
 Tramacet: _____ / _____ : _____ / _____ /10
 Oxycodone: _____ / _____ : _____ / _____ /10
 Hydromorphone: _____ / _____ : _____ / _____ /10
 Naprosyn: _____ / _____ : _____ / _____ /10
 Other: : _____ / _____ : _____ / _____ /10
 _____ / _____ : _____ / _____ /10

Pain scale at departure from recovery (0-10): _____ (time: __:__)

Admission to hospital

No Yes - Why: _____

Complications while in recovery: _____

Patient D/C with antibiotics No
 Yes (Name/Dosage/Frequency x # Days)
_____ / _____ / _____ x _____ d

Patient D/C meds: (Name/Dosage/Frequency x # Days)

- Empracet / _____ / _____ x _____ d
- Tramacet / _____ / _____ x _____ d
- Oxycodone / _____ / _____ x _____ d
- Hydromorphone / _____ / _____ x _____ d
- Naprosyn / _____ / _____ x _____ d

Other: _____ / _____ / _____ x _____ d
_____ / _____ / _____ x _____ d
_____ / _____ / _____ x _____ d

Inform patient how to fill out pain scales at home and how to do it by internet. Give out the sheets but encourage using internet if possible and patient at ease with this.

If willing to use internet:

Get patient email address: _____@_____.

Patient anonymous login name: _____

(first letter of hospital/tree numbers in assigned ID code (Ex if first patient enrolled and at the RVH – anonymous ID # is R001))

Give out their login name for the anonymous internet access and write down on hard copy pain scale sheets that go with patient. Give out hard copy sheets even if patient wants to use internet.

Send email immediately to patient to link to internet forms.

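### The 2-hour pain score is obtained by recall at discharge and Appendix III has no timed 2-hour line; a prompted, time-stamped self-rating would be a cheap improvement

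*Combined protocol and SAP*

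**What the plan says.** Section 5 (data gathering and analysis) describes one interview with the interventional radiologist at discharge. The radiologist goes over the visual analogue chart with the patient and has her rate, from 0 to 10, pain "for the pain felt immediately after the procedure, 2 hours after the procedure has ended, and immediately prior to discharge". Two of these three ratings therefore look back. The same section adds: "The recovery nurses will also have a routine pain scale evaluation prior to giving medication and these will be reviewed".

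Section 1.3 describes local practice as "discharge orders 4-5 hours after the end of the procedure", and Section 7.4 sets a recovery stay of at least 4 hours. On the course of pain, Section 1.3 reports "a maximal pain threshold reached at approximately 2 hours post-procedure, which lasts 3-4 hours". Section 1.4 says that the block's duration of action is one "which can cover the first high pain plateau until the lower pain plateau is reached".

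Appendix III, the recovery-room form, has a clock-timed entry "Pain scale at time of arrival to recovery (0-10"), a matching timed entry at departure, and a time and score beside each drug dose. It has no 2-hour entry.

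Section 3 makes pain a primary objective together with "reduction in use of oral analgesics at home and IV/oral analgesics while in hospital". No primary time point is named. Section 5 expects a "regression analysis of the temporal pain level distribution", and Section 8 allows Student's t-tests on continuous variables.

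**The concern.** Two hours is the scheduled rating nearest the onset of the pain plateau that the block is meant to cover. As written, that rating is a memory of an earlier state, given while the patient is in a different one. The immediate post-procedure rating is recalled too, but Appendix III holds a timed arrival score that can replace it. The 2-hour rating has no timed counterpart.

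The dose-linked scores fill the gap only in part. They exist when a drug is given, so a patient who needs nothing near 2 hours has no real-time score then. In-hospital analgesic use is itself a primary outcome that is expected to fall with the block. The availability of these scores near 2 hours may therefore differ by arm.

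At stake is precision at one clinically central time point. A rating not taken at 2 hours cannot be recovered in analysis.

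**Working it through.** **Timing.** Discharge at 4-5 h minus 2 h gives a recall interval of 2-3 h, and at least 2 h under the 4-hour minimum stay. Maximal pain starts at about 2 h and lasts 3-4 h, so it ends at about 5-6 h. The departure score at 4-5 h usually falls in the same phase and is not recalled.

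**Plan's own figure.** Section 5 uses 7 versus 5, SD 2.5, so d = 2/2.5 = 0.8, with alpha 0.05 and power 80%, and states a total of 42. A noncentral t calculation gives 20.03 per arm one-sided (21 × 2 = 42) and 25.52 per arm two-sided (26 × 2 = 52). So 42 reproduces one-sided only. That is a separate matter. Below I use the two-sided test of Section 8 and the planned 25 per arm; power for one error-free score is then 79.1%.

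**Assumptions not in the documents.** Reliability r of a recalled score 0.6-0.9; within-patient correlation ρ 0.3-0.7; recall error independent of arm and of the other scores; a 2-point difference at every time.

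**Formula.** For a mean of k scores, one of them recalled:

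variance = 2.5² × [k + k(k−1)ρ + (1/r − 1)] / k²

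**2-hour score tested alone (k = 1).** SD = 2.5/√r.
- r = 0.9: SD 2.64, d = 0.759, power 74.8%, loss 4.3 points.
- r = 0.6: SD 3.23, d = 0.620, power 57.4%, loss 21.7 points.

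**Mean of three recovery scores (k = 3), timed arrival score used for the first.**

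| ρ | Power, no recall error | r = 0.9 | r = 0.6 | Loss (points) |
|---|---|---|---|---|
| 0.3 | 96.67% | 96.34% | 94.47% | 0.33-2.20 |
| 0.5 | 92.42% | 91.97% | 89.62% | 0.45-2.81 |
| 0.7 | 87.25% | 86.75% | 84.24% | 0.50-3.01 |

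Worked case, ρ = 0.7 and r = 0.6: 6.25 × (3 + 4.2 + 0.667)/9 = 5.463, so SD = 2.337, against √(6.25 × 7.2/9) = 2.236 without recall error.

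If the recalled immediate rating were averaged in instead of the arrival score, the error term doubles to 2(1/r − 1), and the k = 3 loss becomes 0.7 (ρ = 0.3, r = 0.9) to 6.0 points (ρ = 0.7, r = 0.6).

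**Averaged with the home scores.** Section 7.5 gives 3 × 3 + 7 × 1 = 16 home scores, so k = 19 and the loss is at most 0.07 points. Section 5 instead asks for three a day for up to 10 days, up to 30, so k = 33 and the loss is about 0.02 points or less. A constant 2-point effect over 10 days is unrealistic; these cases show only how far one noisy score is diluted.

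**If the SD of 2.5 already contains recall error,** the loss against plan is zero.

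**The case against.** The strongest reply is that recall is not certain. Section 5 has the radiologist review a chart and the nurses' scores with the patient. The chart is not in the text supplied. It may hold ratings made during recovery, or it may be only the rating scale. This stands as a caveat: if a real-time 2-hour entry exists, a sentence saying so is enough.

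Second, recovery analgesia is described as aggressive, and Appendix III has many dose lines, each with a time and a score. Many patients in either arm may have a real-time score near 2 hours. That is plausible but not assured, because Section 5 describes escalation according to patient need. Unequal availability by arm is a possibility, not a finding.

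Third, the size rests on assumed reliability and correlation, and the plan specifies neither the three-score mean nor the single-score test. This is correct, so no single figure can be claimed and no one scenario bounds the loss.

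A reader might also infer more than the documents support:
- That recall biases the comparison. Nothing shows that recall error differs by arm, and with blinding intact the main effect is noise.
- That midazolam and fentanyl make the recalled score unreliable. No section says that these drugs impair recall of pain.
- That the 2-hour score is the only one that depends on recall. The immediate rating is elicited at the same interview; it merely has a timed substitute.
- That the 2-hour score alone represents the high-pain phase. The departure score usually falls there too.

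**Conclusion.** The point holds as an improvement to data collection; it does not show an error in any stated figure. On the text supplied, the immediate and 2-hour ratings are obtained at discharge, and only the first has a timed, non-recalled counterpart that every patient should have.

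The size depends on an analysis that the plan leaves open. With assumed reliability of 0.6-0.9, 25 per arm and a two-sided test, the loss is negligible when the score is averaged with the home scores, about 0.3-3 points in a mean of three recovery scores (assumed correlation 0.3-0.7), and about 4-22 points if the 2-hour score is tested alone. It is zero against plan if the SD of 2.5 already includes recall error. The expected time-course regression uses many scores, which points towards the smaller end, but no primary time point is named to settle it.

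**What to change.** Have the recovery nurse prompt and time-stamp the patient's own 0-10 rating at 2 hours after the end of the procedure, in both arms and whether or not medication is being given. Add that line to Appendix III. State that this rating and the timed arrival and departure scores are analysed in place of the values recalled at discharge. Keep the dose-linked scores as they are. The reading is for data collection only and changes nothing in the medication regimen.

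If the visual analogue chart named in Section 5 already holds a real-time 2-hour entry, state instead that this entry is the one analysed.

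The cost is one line on an existing form and one extra timed reading per patient, taken within the existing stay of at least 4 hours by nurses who already score pain.
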